3. Friend/Family Share: Index participants who are randomized to have Friend/Family Share ON will give their friend or family member access to their self-monitoring data. Text messages sent by the program bot, which includes the index participant and friend/family member, will use a similar format as described in Group Share ON. The friend or family member will be trained to respond to data in ways that enhance the participant's motivation and self-regulation. If an index participant is randomized to Friend/Family Share OFF, the text messages from the bot will prompt the participant and friend/family member to communicate about the LM program; those messages will be standardized, except for names, and will not be tailored to index participant progress. Index participants will be instructed to refrain from sharing any device data with friends or family members.

Assessments: Index Participants

Research assistants who are blind to study condition will administer assessments remotely at months 0, 3, 6, 12, and 24. These staff members will have no involvement with the intervention. Index participants will be instructed not to disclose information about their treatment condition to assessment staff. Assessment staff will receive training in adherence to the data collection protocol, and their skills will be periodically reassessed for quality control. As compensation for time, index participants will be paid for assessment visits 6, 12, and 24. To enhance retention, study staff will send newsletters and birthday/holiday cards to index participants. Self-report data will be electronically captured and managed through REDCap, a secure web-based research database application.

Primary and secondary outcomes

Weight will be measured using a wireless scale, which is accurate to 0.2 kg. In order to maximize accuracy, we will (1) provide instructions (e.g., place scale on flat, hard surface; weigh upon waking, without clothes, after using the bathroom), (2) require

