
Statistical Analysis

Descriptive statistics and exploratory graphing will be generated for all variables. Data summaries will be produced for the full sample and by condition. Continuous variables will be transformed if necessary. Baseline characteristics will be compared for each ON versus OFF contrast, as well as for each of the 8 study arms, using ANOVAs for continuous variables and a chi-square tests for categorical variables. Key baseline variables that differ by condition will be considered for use as covariates in the analyses described below. Likelihood-based estimation methods and multiple imputation models

will be used to handle missing data.

Aim 1

This study will evaluate the hypotheses that long-term weight loss (primary outcome) and PA and calorie intake (secondary outcomes) will be superior in Coach Share ON vs. OFF; in Group Share ON vs. OFF; and in Friend/Family Share ON vs. OFF. We will model the pattern of change in weight over time using multilevel models. The first level will model individual weight loss over time with baseline as time 0. At the second level, the individual intercept and slope will be entered as outcomes with each of the three types of data sharing examined separately as a predictor. The cross-level interaction between time and type of data sharing (e.g., Coach Share ON vs. OFF) will be used to determine the effect of the partnership factor on the pattern of change in weight. Restricted maximum likelihood will be used to estimate model parameters and to test the significance of random effects. Both linear and higher-order time effects will be examined. Similar multilevel models will separately examine the effect of each of the three partnerships on PA and calorie intake. As an exploratory aim, we also will test the interaction effects of the three data sharing partnerships by adding higher-order interaction terms to the aforementioned multilevel models.

Aim 2

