additional codes based on themes that arise, non-substantive codes, and detailed codes for analysis of specific topics. We will create a coding dictionary based on analysis of the first five transcripts, and every fifth subsequent transcript will be double-coded in order to assess interrater reliability. If there is <90% agreement in coding, we will re-assess domains to identify areas in which different labeling may have been used for similar ideas.

Power analyses suggest that a sample size of 238 is required for 80% power with the significant level of 0.05 and four assessment points, assuming the ratio of the variability of level-1 coefficient to the variability of level-1 residual is at least one. The study is adequately powered with the proposed sample size of 320 with up to 25% attrition.

c) **Withdrawal of Subjects**

Participants will be withdrawn from the research without their consent if there is a change in the subject's medical condition, if all or part of the study is discontinued for any reason by the sponsor, investigator, university authorities, or government agencies, new information is available to the investigator, or there are harmful unforeseen reactions experienced by the participant or other participants in the study. Participants will be notified about any new information that may affect their health, welfare, or choice to stay in the research.

If the friend/family member identified by the index participant does not consent to participate in the study, the index participant will be asked to identify another friend/family member. If they cannot find another friend/family member who would be willing to consent to the study (which is an inclusion criteria), then the index participant will be deemed ineligible and provided with relevant weight loss referrals.

Index participants and friends/family members may withdraw from the study at any time, and it will not be held against them. If an index participant or friend/family member stops being involved in the research, already collected data may not be removed from the study database. Any fee the index participant or friend/family member may be paid will be determined by the amount of time they spend in the trial and, if they do not complete the study, the reason for leaving the study early.

If termination is necessary, the project coordinator will contact the index participant or friend/family member immediately to discuss the grounds for their termination.

2) **Risks to Subjects**

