Several steps will be taken to protect index participant confidentiality in the context of group-based treatment. At the first group meeting the importance of confidentiality will be discussed and concrete guidelines will be provided regarding permissible versus inappropriate disclosure of information about group-based treatment to others, including via social media (e.g., when discussing this LM program with other parties, the focus should be limited to one's own experience, not what is shared by others in group; names and identifying details of other index participants should never be disclosed to others; etc.). To maximize adherence to these guidelines, they will be presented in a way that elicits feedback from the group (so that group members have a sense of ownership

regarding these norms) and index participants will be encouraged to publicly commit in group to upholding these standards of confidentiality. Index participants will be notified that failure to respect the confidentiality of other group members is grounds for dismissal from the program. Similar training about confidentiality will be conducted with designated friends/family members who participate in the program to support an index participant's LM efforts.

3) Potential Benefits to Subjects

Participants may or may not benefit directly from this study. It is possible that the intervention may promote healthy behaviors, such as increasing physical activity and reducing caloric consumption, which may benefit index participants psychologically and medically. Also, the prescribed behavioral changes for index participants are known to promote improved quality of life and positive health outcomes. Participants in LM programs typically report that mood and quality of life also improve during the course of the program.

4) Privacy and Confidentiality

This study will not use nor disclose Protected Health Information (PHI).

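### Withdrawal is written as leaving the research, with no provision for later weights, so participants withdrawn for medical reasons can have avoidable missing outcomes

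*Protocol*

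**What the plan says.** Section c), Withdrawal of Subjects, says that participants will be "withdrawn from the research without their consent if there is a change" in the subject's medical condition. The same sentence lists other triggers, including where "there are harmful unforeseen reactions experienced by the participant or other participants in the study". The medical trigger carries no qualifier of severity or safety. On data, the section says only that "already collected data may not be removed from the study database" when someone stops being involved. Neither this section nor any other says whether weights are collected after an investigator-initiated withdrawal.

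The Risks to Subjects section describes a different kind of removal, with a different object: "failure to respect the confidentiality of other group members is grounds for dismissal from the program". It does not say whether a dismissed person continues with assessments.

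The outcome at stake is the primary one. Under Statistical Analysis, Aim 1, the hypothesis is that "long-term weight loss (primary outcome) and PA and calorie intake (secondary outcomes) will be superior in Coach Share ON vs. OFF", and likewise for the other two sharing factors. Under Assessments: Index Participants, blinded staff "will administer assessments remotely at months 0, 3, 6, 12, and 24", and weight comes from a wireless scale. Missing data are to be handled by "Likelihood-based estimation methods and multiple imputation models".

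**The concern.** Stopping an intervention and stopping measurement are separate decisions. The withdrawal rule joins them, because its object is the research and it makes no provision for later data. Someone withdrawn under it at month 6 or 12 would then have no month-24 weight.

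The protocol itself links the main trigger to the outcome. Its exclusion criteria rule out medical conditions partly because they may change weight. Its Risks section says that losing weight may lead to medication changes or gallstones. The missing weights could therefore belong to people whose later weight differs from that of otherwise similar people who stay.

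This is not a detail that can wait for the statistical analysis plan. Whether weights are collected after someone leaves the programme is settled by protocol and consent, and no analysis can restore weights that were never taken.

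**Working it through.** **1. The plan's own figure.** The power paragraph requires 238 participants and enrols 320, allowing up to 25% attrition.

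- 238 / 0.75 = 317.3, so 318 are needed, against 320 planned. The figure reproduces.
- 320 x 0.75 = 240 retained, 2 above the 238 required.
- Largest attrition that still leaves 238: 1 - 238/320 = 25.6%.

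**2. What a withdrawal would cost.** The Adverse Event Questionnaire is given at months 6, 12 and 24. If an event first reported at month 6 led to withdrawal, the month-12 and month-24 weights would be lost. If first reported at month 12, the month-24 weight would be lost.

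**3. Effect on precision (withdrawal rates assumed).** If 5% were withdrawn, 0.05 x 320 = 16 month-24 weights would go. That is one fifth of the 80 that the 25% allowance covers. If they fall inside the allowance, planned power is unaffected.

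If they came on top of 25% attrition, a scale is needed. The protocol gives no effect size, so I assume a plain two-sided comparison of 119 against 119: d = sqrt(2/119) x (1.960 + 0.842) = 0.363 SD.

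| Extra loss (share of 320) | Retained | Power at d = 0.363 |
|---|---|---|
| 0% | 240 | 80% |
| 2% | 234 | 79% |
| 5% | 224 | 78% |
| 10% | 208 | 75% |

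**4. Effect on the ON-OFF contrast.** Let w be the share withdrawn in a group. Let g be the mean difference, in SD units, between withdrawn participants and comparable retained ones that observed data do not explain. As a difference in month-24 means, the size of the bias is

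|w_ON x g_ON - w_OFF x g_OFF|.

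The document gives no withdrawal rates and no weight SD, so every w and g below is an assumption.

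| w_ON, w_OFF | g | Bias (SD) | Share of 0.363 |
|---|---|---|---|
| 5%, 5% | same in both | 0 | 0% |
| 5%, 2% | 0.25 to 1.0, same in both | 0.0075 to 0.03 | 2% to 8% |
| 10%, 5% | 0.25 to 1.0, same in both | 0.0125 to 0.05 | 3% to 14% |
| 10%, 2% | 0.25 to 1.0, same in both | 0.02 to 0.08 | 6% to 22% |
| 5%, 5% | 0.25 to 1.0, opposite signs | 0.025 to 0.10 | 7% to 28% |

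Example: 0.05 x 1.0 - 0.02 x 1.0 = 0.03 SD. The g in this formula is only what remains after earlier weights and modelled covariates have been used. A raw difference between leavers and stayers would overstate the bias.

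**5. After the fix.** For each participant who agrees to continue, this source of missing weights disappears. The required sample size does not change.

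**The case against.** The best case on the other side has four parts.

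- **No sentence says weight collection stops.** That is true. It is inferred from the object of the withdrawal (the research) and from the absence of any provision for later data. The instruction under Data Management to re-contact people for missing data is general and is not said to cover those withdrawn. The inference is the natural reading, but it remains an inference.
- **The rule may rarely be applied.** A reader might infer that every medical change leads to withdrawal and that such losses will be common. The document does not support that. The Risks section foresees medication adjustment and has participants arrange it with their own physicians. The adverse event questionnaire goes to all participants at three time points, which presumes that many people with medical events remain. No withdrawal rate is given.
- **A link to arm is not shown.** A reader might infer that reactions to being monitored, or dismissals for breaching confidentiality, will fall more heavily on sharing arms and bias the contrast. The trigger is unforeseen harm, whereas shame, critical remarks and relationship strain are listed as foreseen risks. The stated responses to data-sharing problems are coaching or replacing the partner. Dismissal is from the programme, not the research, and group meetings and their confidentiality rules apply in every arm. Some difference is possible, because coaches see device data only under Coach Share ON and regular discussion of sharing concerns is specified only for sharing conditions. That makes it plausible and no more.
- **Withdrawn people are not dropped from the analysis.** A reader might infer that the randomised comparison is broken outright. Data already collected stay, and the multilevel model uses them. Only later weights that earlier data do not predict can cause bias.

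These points limit the size of the concern. They do not remove it: the rule as written makes no provision for later weights, for reasons that the protocol itself ties to weight. The analysis plan is not shown and consent pages were removed, so neither can be checked for wording that softens this.

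**Conclusion.** The point holds as a defect in how the withdrawal rule is fixed. Followed as written, it gives avoidable missing later weights on the primary outcome, for reasons that may be related to weight. Likelihood methods and multiple imputation repair this only in part.

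Its size cannot be stated. Under the assumed inputs, bias in an ON-OFF contrast runs from zero to about 0.10 SD, and most of the settings shown lie well below that upper end. The share-of-effect figures also rest on the assumed d of 0.363. Power falls below plan only if these losses exceed the attrition allowance. The change is worth making because it costs little and protects month-24 weights, not because a material bias has been demonstrated.

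**What to change.** Amend Withdrawal of Subjects, and the matching consent wording, to distinguish stopping the programme from stopping outcome assessment. The text should state that:

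- a participant who stops or is removed from the programme, including by dismissal for a confidentiality breach, is asked to continue the remaining home-scale weights and questionnaires and is kept in the randomised comparison;
- the exceptions are withdrawal of consent, discontinuation of the study, and a judgement by the investigators that continued assessment is itself unsafe;
- the reason for stopping is recorded, and whether it applies to the programme, to assessment or to both.

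The criteria for stopping the programme remain with the investigators; nothing here proposes changing them.

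The cost is revised wording, some follow-up contact (each time point needs four consecutive daily weights with instructions confirmed), and letting these participants keep the scale. Assessments are already remote and scale readings already reach the study portal electronically, so little new procedure is needed.

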Adults attempting weight loss through lifestyle modification (LM) typically find maintenance of behavior change difficult. Outcomes might be improved if participants are provided with sustained sources of accountability and support and ongoing opportunities to reflect with others on goal progress. This study proposes that sharing digital data with other parties has the potential to improve long-term weight loss. The proposed study will enroll adults (“index participants”) (N = 320) with overweight/obesity in a 24-month LM program and instruct them to use digital tools for self-monitoring of weight, physical activity, and eating on a daily basis. Groups will meet remotely each week in months 1-3 to initiate weight loss. In months 4-24, intervention contact will be remote and will include the following: quarterly group meetings held via videoconference; brief phone calls with the coach held twice per quarter; and monthly text messages with the coach, with a small group of fellow group participants, and with a friend or family member outside of the program. Text message content will vary according to treatment condition, i.e. three types of data sharing partnerships: Coach Share, Group Share, and Friend/Family Share. Outcomes will be measured at months 0, 3, 6, 12, and 24. Primary aims include determining if Coach Share, Group Share, and Friend/ Family Share each improve long-term weight loss, PA, and calorie intake, and examining if effects are additive when participants are assigned to engage in more than one type of data sharing partnership. The secondary aim is to explore mediators and moderators of intervention effects. The tertiary aim is to determine how the quality of relationship with coach, group members, and friends/family member over time may differentially moderate treatment effects and predict data sharing efficacy. As digital technology makes data sharing increasingly feasible, it is critical to determine how to optimize these partnerships to improve long-term outcomes in LM.

2) Protocol Title

Sharing Digital Self-Monitoring Data with Others to Enhance Long-Term Weight Loss: A Randomized Trial using a Factorial Design

3) Sponsor / Funding

National Institutes of Health

4) IRB Review History

This is an original IRB submission for this project.

5) Investigator

[name], Principal Investigator
Drexel University

[name], Co-Investigator
Drexel University

[name], Co-Investigator
Rowan University

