[name], Co-Investigator
Drexel University

[name], Co-Investigator
Northwestern University

[name], Co-Investigator
Drexel University

6) Objectives

This study is designed to test new approaches to supporting long-term behavior change. Specifically, this study will test whether using coaches, program peers, or family/friends as sources of support and accountability can improve long-term weight loss.

Aim 1: Test the hypotheses that Coach Share, Group Share, and Friend/Family Share will each improve long-term weight loss (primary outcome) and PA and calorie intake (secondary outcomes) (i.e., outcomes will be compared for participants who are randomized to engage in that type of data sharing partnership, versus those who are not). Exploratory analyses also will determine if effects are partially or fully additive, antagonistic, or synergistic when participants are assigned to more than one type of data sharing partnership.

Aim 2: Test the following mediators of intervention effects: perceived supportive accountability, motivation, self-regulation, self-monitoring engagement, coaching quality, social comparison, and social support.

Aim 3: Determine how quality of the relationship with the coach, group members, and friend/family member over time may differentially moderate treatment effects and predict data sharing efficacy.

7) Background

In the proposed study, adults with overweight/obesity (i.e., “index participants”) will enroll in a 24-month LM program and use digital self-monitoring tools on a daily basis (wireless body weight scale, wearable PA sensor, and app to record dietary intake). In months 1-3, groups will meet remotely every week through videoconferencing to initiate weight loss. Contact in months 4-24 will continue remotely, with group meetings continuing to be held via videoconferencing (once per quarter) and brief, individual phone calls with the coach (twice per quarter). Participants also will exchange monthly text messages with the coach; monthly text messages with a small group of fellow participants; and monthly text messages with a friend or family member outside of the program who will be trained to provide support. A factorial design will be used to efficiently test the independent effects of three types of data sharing partnerships:

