All index participants will receive a 24-month lifestyle modification (LM) intervention. They will receive 20 sessions of group-based behavioral treatment for weight loss. Groups will meet weekly in months 1-3 over the Zoom videoconferencing platform. In months 4-24, one group meeting held over Zoom will take place every 3 months, and two brief (15-minute) individual coach phone calls will occur twice per quarter (14 calls in total over 21 months). During phone calls, coaches will check in about progress towards goals, review core behavioral skills that are most relevant, and collaboratively set goals for the next month. All index participants also will regularly exchange program text messages with the LM coach; with fellow LM participants; and with a designated friend/family member. All index participants will be instructed to use digital self-monitoring devices daily (PA sensor, food record app, smart scale) throughout the program.

Treatment Conditions

The content of the text messages (in particular, whether or not the message includes the participant's digital device data) delivered during months 4-24 will vary according to treatment condition. These three treatment conditions will be provided to 50% of participants, with an equal number of participants randomized to have each of the below three treatment conditions ON or OFF. For example, 160 index participants will have their self-monitoring digital data accessible to their friend/family member, and 160 participants will not have this feature as part of their intervention. Random assignment will be conducted using minimization procedures, which results in better condition balance than simple randomization. Baseline covariates used for randomization will include biological sex and BMI.

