Potential risks to participants are considered minimal. Participants will be informed of all potential risks when providing consent and assent before study participation. However, key personnel will address any discomfort or concerns expressed by the participant in regard to any aspect of the study if they do occur. If participants indicate any substantial distress, then risk assessment will occur and appropriate referrals for treatment will be provided as necessary.

One risk of the program is that as index participants lose weight, they may need to take less of any medications they are on, or they may develop gallstones. Index participants taking any medication will be instructed to carefully coordinate the oversight of these

medications with their primary care physicians to make any necessary adjustments of dosage necessary if weight loss occurs. Gallstones can result if weight is lost too quickly, but our study is designed to help individuals lose weight at only approximately 1-2 pounds per week. When using exercise equipment, however briefly, there is always a risk for injury if adequate precautions are not taken. In addition, PA may be uncomfortable to those index participants who are inactive or overweight, or may cause exacerbation of certain medical conditions. However, this is unlikely given the moderate recommendation (walking). An Adverse Event Questionnaire will be administered to all participants at 6, 12, and 24 months. This questionnaire will collect information about any medical events that have occurred during the course of the program. If an adverse event is reported and more information is necessary, an interview will be conducted with the participant to collect the additional information. This information will then be reported to NIH.

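### Medical adverse events are first asked about systematically at month 6, although an assessment already takes place at month 3, when the weekly phase ends

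*Protocol*

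**What the plan says.** Section 2) Risks to Subjects sets the schedule of the only systematic collection of medical events that the protocol describes: "An Adverse Event Questionnaire will be administered to all participants at 6, 12, and 24 months". The form covers medical events over the program to date. A reported event can lead to an interview, and the information then goes to NIH.

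The same section names the risks. Medication needs may fall as weight falls. On the second risk it says "Gallstones can result if weight is lost too quickly", and it adds that the program aims at about 1-2 lb per week. Injury, discomfort and worsening of existing conditions are linked to physical activity.

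Section 11 g), Assessments: Index Participants, says that research assistants "blind to study condition will administer assessments remotely at months 0, 3, 6, 12, and 24". The opening summary describes the early phase: "Groups will meet remotely each week in months 1-3 to initiate weight loss". Section 11 g), Uniform Components, gives the whole length: "All index participants will receive a 24-month lifestyle modification (LM) intervention".

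Under Withdrawal of Subjects, a participant can be withdrawn without consent if their medical condition changes or if harmful unforeseen reactions occur. No adverse event form at exit is mentioned.

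**The concern.** The most intensive part of the program ends with an assessment by blinded staff, and the safety form is left out of that one assessment. Two of the named medical risks accompany weight loss, and the weekly phase is where weight loss is meant to start. Inactive participants also begin their activity then.

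Two things are at stake. The first is recall: an event from the first weeks may be described nearly six months later, with less accurate timing and detail. The second is loss: a medical event in months 1-3 may be the reason that someone leaves or is withdrawn, and that person is then absent when the first form is given. Loss of this kind would be related to the events being counted, so early events could be under-reported.

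**Working it through.** The protocol states no event rate and no figure that bears on this point, so there is nothing to reproduce. The check compares schedules.

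**Inputs**
- Questionnaire: months 6, 12, 24 (section 2) Risks to Subjects).
- Assessments: months 0, 3, 6, 12, 24 (section 11 g)).
- Group sessions: 20 in total, weekly in months 1-3 and then one per quarter (section 11 g), Uniform Components).
- Attrition allowance: up to 25% of 320 over the study, timing not given (power paragraph of Statistical Analysis).

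**1. Which assessments lack the form.** The post-baseline assessments are 3, 6, 12 and 24, and the form is given at 6, 12 and 24. Only month 3 is left out.

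**2. How concentrated contact is before month 3.** Months 4-24 are 21 months, and 21 / 3 = 7 quarterly sessions. That leaves 20 - 7 = 13 weekly sessions, so 13 / 20 = 65% of group sessions fall in the first 3 of 24 months. If the stated rate held in each of 13 weeks (an assumption), the loss by month 3 would be 13 x 1 to 13 x 2 = 13 to 26 lb. This describes exposure; it is not a count of events.

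**3. Delay to first systematic question.** For onset at month t (0 to 3), the delay is 6 - t now and 3 - t with a month-3 form.

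| Onset (month) | Delay now (months) | Delay with month-3 form (months) |
|---|---|---|
| 0 | 6 | 3 |
| 1.5 | 4.5 | 1.5 |
| 3 | 3 | 0 |

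The range moves from 3-6 months to 0-3, a gain of 3 months for every early event.

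**4. Participants who might never be asked.** The allowance is 0.25 x 320 = 80 index participants over 24 months. Because the timing is not given, the number gone before month 6 could lie anywhere from 0 to 80 within that allowance. As an illustration only, even attrition would give 80 x 6/24 = 20 gone before month 6 and 80 x 3/24 = 10 before month 3. A month-3 form would then reach 20 - 10 = 10 people who are now missed. It would not reach the other 10.

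**5. Whether another channel fills the gap.** The coach log in section 2) is for harms of data sharing, such as strain in a relationship, and the regular coach discussion is described only for conditions in which data are shared. Staff also respond to concerns that participants raise, but no event recording is described there. Neither is a systematic collection of gallstones, medication problems or injuries.

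**The case against.** Several counter-arguments have weight.

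- **The early months are in scope.** The form asks about the program to date, with an interview if needed. This stands: the issue is delay and loss, and no period goes uncovered for those who stay.
- **Six months is not a long interval here.** The later gaps between forms are 12 - 6 = 6 and 24 - 12 = 12 months, so the protocol accepts recall at least as long elsewhere. This also stands. The case for month 3 is that an assessment exists there and that contact is most intensive before it.
- **Other contact may bring events to light.** Weekly groups run in months 1-3, staff re-contact participants for missing data, and section 4) Privacy and Confidentiality refers to a DSMP that is not shown and may contain reporting rules. Hence the wording that leavers may not be asked, and no claim that events reach NIH late.
- **Onset dates may be recorded.** The protocol neither says so nor rules it out, and form content is often kept outside a protocol.

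A reader might also infer three stronger points that the protocol does not support.

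- *That weight loss, and its risks, end at month 3.* The weekly phase is said to initiate weight loss within a 24-month program. The 1-2 lb rate has no end month, and the activity risks continue.
- *That a safety comparison of ON against OFF is diluted by the lead-in months.* The Statistical Analysis section plans no comparison of medical events by condition.
- *That events should be reported as before and after sharing, split at month 4.* Section 11 g) says that the text content "delivered during months 4-24 will vary according to treatment condition", but section 7) Background has the Coach Share coach viewing data for the whole program, and the friend/family subsection counts 24 monthly exchanges over two years, more than 21 months can hold. The start of sharing is not stated consistently enough to support a split.

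**Conclusion.** The point holds as a modest weakness in safety ascertainment. Systematic questioning about medical events begins at month 6 although an assessment exists at month 3. Events in months 1-3 are asked about 3 to 6 months after onset instead of 0 to 3, and participants who leave or are withdrawn before month 6 may not be asked. The delay follows directly from the two schedules. The number of people or events affected cannot be derived: it depends on the timing of attrition and on an event rate, and the protocol gives neither.

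The conclusion assumes that no collection rule in the unseen DSMP already covers months 1-3. It has no bearing on the primary weight outcome, the sample size or the type I error. It is worth acting on because the remedy is cheap.

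**What to change.** In section 2) Risks to Subjects, schedule the same Adverse Event Questionnaire at months 3, 6, 12 and 24. Have each form ask about events since the participant's last completed form (since enrollment if there is none), and record an onset date for every event. Asking since the last form also avoids the same event being reported again under the present whole-program wording. Onset dates allow events to be placed in time without fixing a boundary for when sharing starts.

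The cost is one more administration of an existing form at an existing assessment: a few minutes per participant and some added event follow-up. Two limits remain. Section 6) Subject Compensation pays for months 6, 12 and 24 only, so completion at month 3 may be lower, and anyone who leaves before month 3 is still not reached. The change can help only participants who have not yet passed month 3.
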